## **12.2. Study monitoring by the contracted research organisation**

The CRO Site Monitor will monitor the study to verify that, amongst others, the:

- Data are authentic, accurate, and complete.
- Safety and rights of subjects are being protected.
- Study is conducted in accordance with the currently approved protocol, any other study agreements, GCP and all applicable regulatory requirements.

The Investigator and the head of the medical institution (where applicable) agrees to allow the monitor direct access to all relevant documents.

The Investigator must ensure provision of reasonable time, space and qualified personnel for monitoring visits.

Direct access to all study-site related and source data is mandatory for the purpose of monitoring review. The monitor will perform an eSource review.

Upon completion or premature discontinuation of the study, the monitor will conduct site closure activities with the Investigator or site staff, as appropriate, in accordance with applicable regulations, GCP, and GSK procedures.

## **12.3. Record retention**

Following closure of the study, the Investigator must maintain all site study records (except for those required by local regulations to be maintained elsewhere) in a safe and secure location. The records must be easily accessible, when needed (*i.e.*, audit or inspection), and must be available for review in conjunction with assessment of the facility, supporting systems, and staff. Where permitted by applicable laws/regulations or institutional policy, some or all of these records can be maintained in a validated format

other than hard copy (*i.e.*, microfiche, scanned, electronic); however, caution needs to be exercised before such action is taken. The Investigator must ensure that all reproductions are legible and are a true and accurate copy of the original and meet accessibility and retrieval standards, including re-generating a hard copy, if required. Furthermore, the Investigator must ensure that an acceptable back-up of the reproductions exists and that there is an acceptable quality control procedure in place for making these reproductions.

GSK will inform the Investigator/institution of the time period for retaining these records to comply with all applicable regulatory requirements. However, the Investigator/institution should seek the written approval of the sponsor before proceeding with the disposal of these records. The minimum retention time will meet the strictest standard applicable to a particular site, as dictated by ICH GCP, any institutional requirements, applicable laws or regulations, or GSK standards/procedures.

The Investigator/institution must notify GSK of any changes in the archival arrangements, including, but not limited to archival at an off-site facility, transfer of ownership of the records in the event the Investigator leaves the site.

#### **12.4. Quality assurance**

To ensure compliance with GCP and all applicable regulatory requirements, GSK may conduct a quality assurance audit. Regulatory agencies may also conduct a regulatory inspection of this study. Such audits/inspections can occur at any time during or after completion of the study. If an audit or inspection occurs, the Investigator and institution agree to allow the auditor/inspector direct access to all relevant documents and to allocate his/her time and the time of his/her staff to the auditor/inspector to discuss findings and any relevant issues.

#### **12.5. Posting of information on publicly available clinical trial registers and publication policy**

Study information from this protocol will be posted on publicly available clinical trial registers before enrolment of subjects begins.

Summaries of the results of GSK interventional studies (Phase 1 to 4) are posted on publicly available results registers within 6 months of the primary completion date for studies of authorised vaccines and 18 months for studies of non-authorised vaccines.

GSK also aims to publish the results of these studies in the searchable, peer reviewed scientific literature. Manuscripts are submitted for publication within 24 months of the last subject's last visit. At the time of publication, this protocol will be fully disclosed.

#### **12.6. Provision of study results to Investigators**

Where required by applicable regulatory requirements, an Investigator signatory will be identified for the approval of the study report. The Investigator will be provided reasonable access to statistical tables, figures, and relevant reports and will have the opportunity to review the complete study results at a GSK site or other mutually-agreeable location.

GSK Biologicals will also provide the Investigator with the full summary of the study results. The Investigator is encouraged to share the summary results with the study subjects, as appropriate.

### 13. COUNTRY SPECIFIC REQUIREMENTS

Not applicable.

## APPENDIX A    LABORATORY ASSAYS

### Anti-EBOV GP IgG ELISA

Blood samples for antibody determination will be collected at indicated timepoints and serum will be separated and frozen at  $-20^{\circ}\text{C}$ .

Antibody level will be determined by evaluating antibody (IgG) responses specific for Zaire Ebola Virus Glycoprotein (EBOV GP) using the ELISA developed by Battelle and JVAP/USAMRIID and transferred to Quest (Focus) laboratory.

Briefly, microtiter plates are coated with the purified recombinant Zaire GP (rGP) specific to the Kikwit-95 strain (the Non-Human Primates (NHP) challenge strain). This strain is 98.5% identical to the vaccine Mayinga EBOV strain (11 aa mismatched) and is 97.5% identical to the isolated Guinea 2014 virus strain (17 aa mismatched). Serial diluted test samples, 2 serial-diluted controls (one QC-high and one QC-low) and a negative sample control (composed of pooled normal human serum purchased from a commercial source) are allowed to incubate in the GP coated wells allowing GP specific antibodies to bind. Additionally, a two-fold serial diluted reference standard, obtained from a vaccinated donor, is included in duplicate. Each well is then incubated with goat anti-human IgG horseradish peroxidase conjugate (HRP). TMB substrate is added to each well and the enzymatic reaction is stopped with a sulfuric acid solution. The color change is then read in a plate reader and sample titers are based on the standard curve calculated using a 4 parameter logistic curve fit. Results are reported in ELISA units/ml (EU/ml). A 2nd generation human standard (microgram/mL) will be evaluated and bridged to the current standard.

This assay will be qualified at Quest Diagnostics laboratories before starting the clinical testings.

### ChAd3-EBO-Z specific CD4+ or CD8+ T-cells

T-cell response will be measured by ICS. In brief, peripheral blood mononuclear cells (PBMCs) are prepared by standard Ficoll-Paque Plus centrifugation and stored frozen in heat-inactivated foetal calf serum containing 10% dimethylsulfoxide. *In vitro* re-stimulation of the PBMCs is performed using a pool of peptides corresponding to the open reading frames of the vaccine GP insert. CD4+ and CD8+ T-cells expressing immune markers such as IFN- $\gamma$  and/or TNF- $\alpha$  and/or IL-2 are detected by flow cytometry. The method has been qualified at NVITAL laboratories.

### ChAd3 neutralising antibodies

In the process of evaluation of the pre-existing or vaccine-induced antibody response against ChAd3, it is of interest to quantify the neutralising antibody concentrations. Neutralising antibodies are antibodies with a capacity to block functional epitopes on the adenovirus, thereby blocking the entry of the virus to the target cells.

This method utilizes serotype-specific, replication incompetent adenovirus, which has an inserted luciferase reporter gene, as described [Paris, 2014; Sprangers, 2003]. Briefly, A549 human lung carcinoma cells are plated in 96-well plates and infected with E1-deleted replication-incompetent rAd-luciferase reporter construct. For each sample, a

total of seven 2-fold serial dilutions are tested in triplicate. Following a 24-hour incubation, the luciferase activity in the cells is measured using the Steady-Glo luciferase reagent system (Promega). 90% neutralisation titres are defined as the maximum serum dilution that neutralised 90% of luciferase activity. GMTs are calculated at pre- and/or post-vaccination and a positive response is defined as any increase in ChAd3 post-vaccination. The exceptions are those with pre-vaccination titres at the upper limit of quantitation (8748). The assay has been qualified for Ad5 and adapted for ChAd3 at NVITAL laboratories.

**APPENDIX B      CLINICAL LABORATORIES (*Amended*  
*06 May 2015*)****Table 24      Outsourced laboratories**

Laboratory	Address
NIAID Vaccine Immune T-Cell and Antibody Laboratory (NVITAL)	[name] [name] 20878 United States
Quest Diagnostics	Focus Diagnostics Clinical Trials, Inc. (d/b/a Quest Diagnostics) [name] [name], United States

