##### 14.1.2.1. Derivations

Refer to Section 14.1.1.1: Derivations for relevant derivations, the following information is specific to the ChAd3 neutralisation data:

- Log-transformed titre values and serological status:
  - o The relevant cut-off value is the reciprocal titre of 12.
- Response:
  - o Yes:  
For seronegative pre-vaccination: Post-vaccination titre value of at least the assay cut-off\* value.

---

Document: CHAD3-004-EBO-Z\_Interim\_Final\_SAP\_v2\_0  
Author: PPD Version Number: 2.0 Version Date: 14JUN2017

Template No: CS\_TP\_BS016 – Revision 3  
Effective Date: 01May2012

Reference: CS\_WI\_BS005

For seropositive pre-vaccination: Post-vaccination titre value of at least x-fold\* increase over the pre-vaccination titre value. o No:

For seronegative pre-vaccination: Post-vaccination titre value of less than the assay cut-off\* value.

For seropositive pre-vaccination: Post-vaccination titre value of less than x-fold\* increase over the pre-vaccination titre value.

NOTE: Assay cut-off value is defined as 12.

NOTE: x-fold is defined as 3-fold.

- Above threshold:
  - o Yes:  
Post-vaccination value  $\geq$  defined threshold.
  - o No:  
Post-vaccination value  $<$  defined threshold.
  - o The threshold value is 200.

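### SAP v2 always scores a child whose pre-vaccination ChAd3 titre is at the assay's upper limit (8748) as a non-responder, although the protocol excepts such children and the SAP declares no change

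*Protocol*

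**What the plan says.** **Protocol, Appendix A (ChAd3 neutralising antibodies).** The assay paragraph says that a "total of seven 2-fold serial dilutions are tested in triplicate". It defines the titre as a dilution step: "90% neutralisation titres are defined as the maximum serum dilution that neutralised 90% of luciferase activity". On response it says that "a positive response is defined as any increase in ChAd3 post-vaccination", and goes straight on: "The exceptions are those with pre-vaccination titres at the upper limit of quantitation (8748"). It does not say how the excepted children are to be treated. It gives no first dilution.

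**Protocol, main text.** Section 11.6 leaves the assay cut-off to the laboratory, before the analysis. Section 11.9 plans vaccine response rates without defining a response, so Appendix A is the only place where the protocol defines a ChAd3 response.

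**SAP v2, section 14.1.2.1.** "The relevant cut-off value is the reciprocal titre of 12", repeated for the response rule as "NOTE: Assay cut-off value is defined as 12". A child who is seronegative before vaccination responds by reaching the cut-off. A seropositive child responds only with a sufficient fold increase, and "NOTE: x-fold is defined as 3-fold". Anything less is scored No. Neither SAP version mentions 8748 or any upper limit for this assay.

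**SAP v2, sections 14.1.1 and 14.1.2.** The ChAd3 tables follow the anti-GP tables, whose response percentages use all children with both a pre- and a post-vaccination result.

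**SAP v2, section 3.3.** The entry under changes to the analysis from the protocol is the single word *None*.

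**The concern.** The protocol foresaw that a rise cannot be observed in a child who starts at the assay ceiling, and made an exception. The SAP drops that exception while tightening the rule from any increase to a 3-fold increase. Followed as written, it records a negative result that comes from the measuring range and not from the child. The section meant to disclose departures from the protocol says that there are none.

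What is at stake is the ChAd3 response table, and to a lesser degree the geometric mean titres (GMTs), which are cut off at the limit with no count of how many values sit there. The children concerned would be those with the strongest pre-existing vector immunity. One tertiary objective is to describe that immunity, so a reader of the response table should be able to see how they were handled.

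Separately, the dilution factor in Appendix A does not match the two limits that the documents give. A reader therefore cannot confirm from the text which titres the assay can report.

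**Working it through.** **Inputs**
- Number of dilutions 7, stated step 2-fold, upper limit 8748, response rule and exception: Protocol Appendix A.
- Cut-off 12 and response factor 3: SAP v2 section 14.1.2.1.
- About 30 children per age stratum per group, 90 per group, 180 in all: Protocol sections 4.2 and 5.2.3.

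**Step 1: does the stated series reproduce the stated upper limit?**
Highest titre = first dilution × step^(7 − 1). Taking 12 as the first dilution (an inference, not stated):
- 2-fold: 12, 24, 48, 96, 192, 384, 768. The last value is not 8748.
- 3-fold: 12, 36, 108, 324, 972, 2916, 8748. The last value equals the stated limit exactly.

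Solving for the step gives (8748/12)^(1/6) = 729^(1/6) = 3. Running seven 2-fold dilutions down from 8748 gives a first dilution of 8748/2^6 = 136.7, which is above the cut-off of 12. And log2(729) = 9.51 is not a whole number, so no number of 2-fold steps joins 12 and 8748.

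**Step 2: the largest rise that can be observed.**
Maximum fold rise = 8748 / baseline, assuming that no titre above 8748 is reported.
- Baseline 2916: 8748/2916 = 3.0, so the rule can just be met.
- Baseline 8748: 8748/8748 = 1.0, so the rule can never be met.
- In general, a 3-fold rise needs a baseline of at most 8748/3 = 2916.

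**Step 3: how far the two response rules differ otherwise.**
If titres are discrete steps of a 3-fold series, the smallest possible rise from a seropositive baseline is one step, which is 3-fold. Any increase and a 3-fold increase are then the same rule for seropositive children, and 8748 is the only baseline above 2916. The missing exception is the one remaining difference. If titres are interpolated, the rules differ for rises between 1-fold and 3-fold, and baselines between 2916 and 8748 also cannot reach 3-fold.

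**Step 4: size of the effect on a response rate.**
Let n children have both results, k of them at 8748 before vaccination, and r respond. The SAP reports r/n; with the exception applied by exclusion it is r/(n − k). The difference, rk/[n(n − k)], is largest when all the others respond (r = n − k), and is then k/n. The documents do not give k, so it is shown as a range:

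| k at 8748 | n = 30 | n = 90 |
|---|---|---|
| 0 | 0 | 0 |
| 1 | 3.3 points | 1.1 points |
| 2 | 6.7 points | 2.2 points |
| 3 | 10.0 points | 3.3 points |

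**Step 5: what the ceiling does not touch.**
Serological status uses 12, and for the threshold table "The threshold value is 200". Both lie far below 8748, so neither classification changes for a child at the ceiling.

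**The case against.** The strongest reply is that almost nothing follows in practice. Protocol section 1.1.3 reports low ChAd3 seroprevalence and low titres where antibodies are present, so the number of children at 8748 may be zero. The endpoint is tertiary, descriptive and confined to about 180 children. The tertiary endpoint is the titre itself, not a responder rate. The effect of pre-existing immunity on Ebola-specific responses is studied by Spearman correlation of baseline titres with Day 30 results (SAP v2 section 14.1.2); the responder rule does not enter it, and children at the ceiling are simply tied at the top rank. The wording about any increase stands only in an assay appendix. All of this stands, and it limits the size of the point. It does not remove it: the SAP rule contradicts the only ChAd3 response definition in the protocol, in the one situation that the protocol singled out.

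On the dilution series, the reply is that 12 and 8748 come from different documents and that nothing says 12 is the lowest dilution tested. That also stands. The exact fit of 12 × 3^6 makes a slip in the word 2-fold the likely explanation, but it remains an inference.

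A reader might go further and infer that the assay tops out at 768, so that many titres pile up there. The documents do not support this. The protocol itself states the upper limit as 8748, and 768 appears nowhere; it arises only by combining the 2-fold wording with an assumed first dilution of 12.

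**Conclusion.** The point holds as a minor inconsistency. SAP v2 omits the protocol's exception for children with a pre-vaccination titre at 8748, replaces any increase with a 3-fold rise, and records no change in section 3.3. Any child at the ceiling is scored as a non-responder regardless of the true response. Each such child costs at most about 3.3 percentage points in an age-by-group cell of 30, or 1.1 points in a group of 90, and the number of such children is unknown and probably small. This rests on titres not being reported above 8748, for example after further dilution.

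The text on seven 2-fold dilutions cannot be squared with limits of 12 and 8748 if 12 is the first dilution.

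Two broader readings should not be drawn. One is that the vector-immunity objective as a whole is compromised: the endpoint is the titre, and the correlation analysis does not use the response rule. The other is that the 3-fold rule by itself lowers response rates: with discrete 3-fold titres it coincides with any increase for seropositive children.

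**What to change.** - **SAP section 14.1.2.1:** carry over the exception. Leave children with a pre-vaccination titre at 8748 out of the response denominator and report their number. The protocol does not say how excepted children are handled, so state this choice explicitly.
- **Titre type:** state whether titres are discrete or interpolated. If interpolated, also report how many children have a baseline above 2916, who cannot reach 3-fold. Excluding them too would be a wider rule than the protocol's exception and should not be presented as restoring it.
- **GMT tables:** report the number of titres at the upper limit beside each GMT.
- **SAP section 3.3:** list the change from any increase to a 3-fold increase.
- **Protocol Appendix A:** check the dilution series against the laboratory's procedure, so that first dilution, step and upper limit agree.

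The cost is one protocol clarification and a few lines of SAP text and table footnotes. The response denominator may become slightly smaller, and the children left out would be the most pre-immune, which is why their number should be shown.

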## APPENDIX C ACCEPTABLE LIMITS FOR ELIGIBILITY AND TOXICITY GRADING SCALES FOR HAEMATOLOGY/ BIOCHEMISTRY PARAMETERS (*Amended 06 May 2015*)

ADULTS AND ADOLESCENTS > 12 YEARS OLD

Table 25 outlines the acceptable limits for eligibility when considering laboratory Screening values.

**Table 25 Acceptable limits/normal ranges for eligibility determination (*Amended 06 May 2015*)**

Haemoglobin (g/dL)	≥ 11 (males) or ≥ 9.5 (females)
Platelet count (x10  /μL)	≥ 100
Total white cell count (x10  /μL)	≥ 2.75
Creatinine (mg/dL)	< 1.5
ALT (IU/L)	< 60 (males) or < 40 (females)

ALT = alanine aminotransferase

Blood safety results at each planned timepoint will be presented per study group according to the toxicity grading scale presented in Table 26. In addition, for haematological values, changes at post vaccination timepoints relative to baseline will be presented per study group.

**Table 26 Toxicity grading scales for hematology/ biochemistry parameters**

Test	Grade 1	Grade 2	Grade 3	Grade 4
Haemoglobin, male (g/dL)	10 to 10.9	9 to 9.9	8 to 8.9	< 8
Haemoglobin, female (g/dL)	8.5 to 9.4	7.5 to 8.4	6.5 to 7.4	< 6.5
Platelets (x10  /μL)	75 to 100	50 to 74.999	25 to 49.999	< 25
WBC – decrease (x10  /μL)	2 to 2.749	1.50 to 1.999	1 to 1.499	<1
Creatinine (mg/dL)	1.5 to 1.7	> 1.7 to 2	> 2.0 to 2.5	> 2.5
ALT increase by factor	1.1 to 2.5xULN	> 2.5 to 5.0xULN	> 5.0 to 10xULN	> 10xULN

ALT = alanine aminotransferase; ULN = upper limit of the normal range; WBC = white blood cells

Note: acceptable limits for eligibility and grading scale adapted from Division of AIDS table for grading severity of adult and pediatric adverse events December 2004; WHO Toxicity Grading Scale for Determining Severity of Adverse Events, February 2003; Toxicity Grading Scale for Healthy Adult and Adolescent Volunteers Enrolled in Preventive Vaccine Clinical Trials, Guidance for Industry, 2007.

**CHILDREN  $\leq$  12 YEARS OLD**

Table 27 outlines the acceptable limits for eligibility when considering laboratory Screening values.

**Table 27 Acceptable limits/normal ranges for eligibility determination**

Haemoglobin (g/dL)	$\geq 8.5$
Platelet count ( $\times 10^3/\mu\text{L}$ )	$\geq 100$
Total white cell count ( $\times 10^3/\mu\text{L}$ )	$\geq 4$
Creatinine (mg/dL)	$< 1.2$
ALT (IU/mL)	$< 60$ (males) or $< 40$ (females)

ALT = alanine aminotransferase

Blood safety results at each planned timepoint will be presented per study group according to the toxicity grading scale presented in Table 28. In addition, for haematological values, changes at post vaccination timepoints relative to baseline will be presented per study group.

**Table 28 Toxicity grading scales for hematology/ biochemistry parameters**

Test	Grade 1	Grade 2	Grade 3	Grade 4
Haemoglobin (g/dL)	7.5 to 8.49	6.5 to 7.49	5 to 6.49	$< 5$
Platelets ( $\times 10^3/\mu\text{L}$ )	75 to 99.999	50 to 74.999	25 to 49.999	$< 25$
WBC ( $\times 10^3/\mu\text{L}$ )	2.5 to 3.999	1.50 to 2.499	1 to 1.499	$< 1$
Creatinine (mg/dL)	1.2 to 1.7	$> 1.7$ to 2.1	$> 2.1$ to 2.5	$> 2.5$
ALT increase by factor	1.1 to 2.5xULN	$> 2.5$ to 5.0xULN	$> 5.0$ to 10xULN	$> 10\text{xULN}$

ALT = alanine aminotransferase; ULN = upper limit of the normal range; WBC = white blood cells

Note: acceptable limits for eligibility and grading scale adapted from Division of AIDS table for grading severity of adult and paediatric adverse events December 2004; WHO Toxicity Grading Scale for Determining Severity of Adverse Events, February 2003; Toxicity Grading Scale for Healthy Adult and Adolescent Volunteers Enrolled in Preventive Vaccine Clinical Trials, Guidance for Industry, 2007.

**APPENDIX D AMENDMENTS AND ADMINISTRATIVE  
CHANGES TO THE PROTOCOL**

GlaxoSmithKline Biologicals	
Vaccine Value & Health Science (VVHS)	
Protocol Amendment 1	
eTrack study number and Abbreviated Title	202090 (EBOLA Z CHAD3-004)
IND number	To be decided
EudraCT number	2014-004714-28
Amendment number	Amendment 1
Amendment date	29 December 2014
Co-ordinating author	PPD [REDACTED], Quintiles, Medical Writing

Rationale/background for changes:
 
 
• For robustness of safety monitoring, the GSK Biologicals' internal safety review committee (iSRC) was replaced by an independent data monitoring committee (IDMC).
 
• Indicate that safety and reactogenicity data will be collected in 100 adults after 1 week of follow-up (study EBOLA Z CHAD3-005) before commencing the current study.
 
• Indicate that safety and reactogenicity data obtained in the context of the age de-escalation process may lead to the selection of a lower ChAd3-EBO-Z vaccine dose in the younger age groups.
 
• Clarify that informed assent will be asked from all subjects in the oldest age stratum (13 to 17 years of age) and from younger subjects as per local requirements.
 
• Define grading scales for local injection site redness/ swelling per age stratum.
 
• Clarify that analysis of safety will be done on the total vaccinated cohort (TVC) and that no according-to-protocol (ATP) cohort for safety will be defined.
 
• Include information on the anti-GP ELISA testing (laboratory, test description).
 
 
In addition, some minor modifications/ clarifications were made.
	

Amended text has been included in ***bold italics*** and deleted text in ~~striketrough~~ in the following sections:

